13. STUDY TERMINATION

The study will be terminated following approval by the FDA of simufilam for the treatment of Alzheimer's disease or at any time at the discretion of the Sponsor.

14. DATA COLLECTION, RETENTION AND MONITORING

14.1. CASE REPORT FORMS

The CRF will be provided as an Electronic Data Capture (EDC) system that will serve as the collection method for subject data. The subjects in the study will not be identified by name on any study documents to be collected by the Sponsor (or CRO designee) but will be identified by a unique subject number.

All clinical information requested in this protocol will be recorded in the EDC system. It is strongly recommended that data entry be completed within 48 hours of a subject's visit. In case of error noted on paper source documents, the correction will be noted, initialed and dated.

EDC data must be reviewed and verified for accuracy and signed-off by the staff personnel before database lock. Paper source documents, if used, will remain at the Investigator's site at the completion of the study.

14.2. AVAILABILITY AND RETENTION OF INVESTIGATIONAL RECORDS

The Investigator must make study data accessible to the monitor, other authorized representatives of the Sponsor (or designee) and Regulatory Agency (e.g., FDA) inspectors upon request. To assure accuracy of data collected in the EDC, it is mandatory that Sponsor representatives have access to original source documents (e.g., subject records, subject charts, and laboratory reports). During review of these documents, the subject's anonymity will be maintained with adherence to professional standards of confidentiality and applicable laws. A file for each subject must be maintained that includes the signed ICF and all source documentation related to that subject. The Investigator must ensure the reliability and availability of source documents for the EDC.

Investigators are required to maintain all study documentation until notification by the Sponsor that any records may be discarded.

The Investigator is responsible for maintaining adequate case histories in each subject's source records.

14.3. SUBJECT CONFIDENTIALITY

All reports and subject samples will be identified only by the assigned subject number and initials, as applicable by local law, to maintain subject confidentiality. Additional subject confidentiality measures (as required by region) will be covered within the Clinical Trial Agreement for each site as applicable.

14.4. LIABILITY

In the event of a side effect or injury, appropriate medical care as determined by the Investigator, or his/her designated alternate will be provided.

If a bodily injury is sustained resulting directly from the study drug, the Sponsor will reimburse for reasonable physician fees and medical expenses necessary for treatment of only the bodily injury that is not covered by the subject's medical or hospital insurance, provided that the injury is not due to a negligent or wrongful act or omission by the study doctor and his/her staff. No other compensation of any type will be provided by the Sponsor. Compensation for lost wages, disability or discomfort due to the study is not available.

14.5. ETHICAL AND LEGAL ISSUES

The Investigator and site personnel are responsible for conducting this study in accordance with the ICH, GCP, and all other applicable laws and regulations.

14.5.1. Institutional Review Board / Ethics Committee

The protocol, ICF, clinical sites and Investigators must be approved by an IRB/EC before the study is initiated. The IRB/EC must comply with U.S. CFR 21 Part 56 or local regulatory and ICH requirements if outside the United States.

Documentation of approval by the designated central IRB will be provided to the Investigators. The Sponsor will:

- Obtain IRB approval of the protocol, ICF, advertisements to recruit subjects and IRB approval of any protocol amendments and ICF revisions before implementing the changes.
- Provide the IRB with any required information before or during the study.
- Submit progress reports to the IRB, as required, requesting additional review and approval, as needed; and provide copies of all relevant IRB communications to the Investigator.

The Investigator is responsible for:

- Notifying the IRB within 15 calendar days of all SAEs and unexpected AEs related to study medications.
- Obtaining approval by their institution's own IRB if the Investigator's institution has its own IRB.

14.6. INFORMED CONSENT FORM

The Sponsor will submit the Informed Consent Form (ICF) to the central IRB for approval. An IRB-approved copy of the ICF will be forwarded to the Investigator and/or site staff.

The ICF documents study-specific information the Investigator provides to the subject and the subject's agreement to participate. The Investigator explains in plain terms the nature of the study along with the aims, methods, anticipated benefits, potential risks, and any discomfort that participation may entail. The ICF must be signed and dated before the subject enters the study. The original ICF and any amended ICF, signed and dated, must be retained in the subject's file at the study site and a copy must be given to the subject.

15. INVESTIGATOR RESPONSIBILITIES

The Investigator agrees to:

- Conduct the study in accordance with the protocol, except to protect the safety, rights, or welfare of subjects.
- Personally conduct or supervise the study.
- Ensure that requirements for obtaining informed consent and IRB review and approval comply with ICH, CFR 21 Parts 50 and 56, or local regulatory and ICH requirements if outside of the United States.
- Report to the Sponsor any AEs that occur during the study in accordance with ICII, CFR 21 Part 312.64, and local laws.
- Read and understand the Investigator's Brochure including potential risks and side effects of the study drug.
- Ensure that all associates, colleagues, and employees assisting in the conduct of the study are informed about their obligations in meeting the above commitments.
- Maintain adequate records in accordance with ICH, 21 CFR Part 312.62, and local laws and have records available for inspection by the Sponsor, FDA, or other authorized agency.

[figure not shown]
- Promptly report to the IRB and the Sponsor all changes in research activity and unanticipated problems involving risks to subjects or others (including amendments and expedited safety reports).
- Comply with all other requirements regarding obligations of Clinical Investigators and all other pertinent requirements listed in ICH, 21 CFR Part 312 and local laws.

17. APPENDIX A – STUDY DESIGN SCHEMATIC

[figure not shown]
A. New / Active Participants

*Includes: AE, Conmeds, Vital Signs, Brief PhysEx, Brief NeuroEx, Height, Weight, C-SSRS, Drug Dispensation (except Re-entry Week 4) and Drug Accountability

** For active participants, HbA1c is only collected if a sample was collected at Study Day 1.

B. Re-entry Participants

18. APPENDIX B – SCHEDULE OF ACTIVITIES FOR NEW/ACTIVE PARTICIPANTS

| Procedures | Study Day 1 | Wk 4 | Wk 16 | Wk 28 | Wk 40 | Wk 52 | Repeat Visit A ⁵ | Repeat Visit B ⁶ | EoT/Early Term | Follow-up Phone Call ⁸ |
|--------------------------------------|----------------|------|-------|----------------|-------|----------------|-----------------------------|-----------------------------|----------------|-----------------------------------|
| Informed Consent | X | | | | | | | | | |
| I/E Criteria | X | | | | | | | | | |
| Adverse Events | X | X | X | X | X | X | X | X | X | X |
| Concomitant Medications | X | X | X | X | X | X | X | X | X | |
| Vital Signs | X | X | X | X | X | X | X | X | X | |
| Brief Physical Examination | X | X | X | X | X | X | X | X | X | |
| Brief Neurologic Examination | X | X | X | X | X | X | X | X | X | |
| Height | X | X | X | X | X | X | X | X | X | |
| Weight | X | X | X | X | X | X | X | X | X | |
| Resting ECG | X | X | | X | | X | | X | X | |
| Biochemistry, Hematology, Urinalysis | X | X | | X | | X | | X | X | |
| HbA1c | X | | | X ⁴ | | X ⁴ | | X ⁴ | X ⁴ | |
| Plasma Biomarkers ¹ | X | | | X | | X | | X | X | |
| CDR | X | | | X | | X | | X | X ⁷ | |
| C-SSRS ² | X | X | X | X | X | X | X | X | X | |
| Study Drug Dispensation | X ³ | X | X | X | X | X | X | X | | |
| Study Drug Accountability | | X | X | X | X | X | X | X | X | |
| End of Study Follow-up Phone Call | | | | | | | | | | X |

¹Plasma Biomarker collection will begin upon receipt of required supplies.

²On Study Day 1, as well as all remaining visits, the ‘C-SSRS Since Last Visit’ version will be administered.

³The first dose of study drug is administered at the clinic to all subjects on Study Day 1 at least four hours after any prior dose and at least one hour before departure.

⁴HbA1c should only be collected in subjects with a Study Day 1 HbA1c.

⁵Repeat Visit A occurs 12 weeks following the Week 52 visit and then reoccurs every 24 weeks thereafter.

⁶Repeat Visit B occurs 12 weeks following the first Repeat Visit A visit and then reoccurs every 24 weeks thereafter.

⁷CDR is only performed at the End of Treatment visit.

⁸Follow-up phone call occurs 1-2 weeks after End of Treatment/Early Termination.

19. APPENDIX C – SCHEDULE OF ACTIVITIES FOR RE-ENTRY PARTICIPANTS

| Procedures | Re-entry Day 1 | Re-entry Wk 4 ⁵ | Repeat Visit A ⁶ | Repeat Visit B ⁷ | EoT / Early Term | Follow-up Phone Call ⁸ |
|--------------------------------------|----------------|----------------------------|-----------------------------|-----------------------------|------------------|-----------------------------------|
| Informed Consent | X | | | | | |
| Medical History | X | | | | | |
| I/E Criteria | X | | | | | |
| Adverse Events | X | X | X | X | X | X |
| Concomitant Medications | X | X | X | X | X | |
| Vital Signs | X | X | X | X | X | |
| Brief Physical Exam | X | X | X | X | X | |
| Brief Neurologic Exam | X | X | X | X | X | |
| Height | X | X | X | X | X | |
| Weight | X | X | X | X | X | |
| Resting ECG | X ¹ | X | | X | X | |
| Biochemistry, Hematology, Urinalysis | X ¹ | X | | X | X | |
| HbA1c | X | | | X | X | |
| Plasma Biomarkers ² | X | | | X | X | |
| CDR | X ¹ | | | X | X ⁸ | |
| C-SSRS ³ | X | X | X | X | X | |
| Study Drug Dispensation | X ⁴ | | X | X | | |
| Study Drug Accountability | | X | X | X | X | |
| End of Study Follow-up Phone Call | | | | | | X |

¹Resting ECG, Biochemistry, Hematology, Urinalysis, and CDR to be performed only for Re-entry Day 1 subjects who completed the PTI-125-10 Week 52 visit >60 days prior to re-entry.

²Plasma Biomarker collection will begin upon receipt of required supplies.

³On Re-entry Day 1, as well as all remaining visits, the ‘C-SSRS Since Last Visit’ version will be administered.

⁴The first dose of study drug is administered at the clinic to all subjects at least one hour before departure.

⁵Re-entry Week 4 visit performed only for Re-entry subjects who completed PTI-125-10 Week 52 visit >60 days prior to re-entry.

⁶Repeat Visit A occurs 12 weeks following the Re-entry Day 1 visit and then reoccurs every 24 weeks thereafter.

⁷Repeat Visit B occurs 12 weeks following the first Repeat Visit A and then reoccurs every 24 weeks thereafter.

⁸CDR is only performed at the End of Treatment visit.

⁹Follow-up phone call to occur 1-2 weeks after End of Treatment/Early Termination.

[figure not shown]

# **Document History**

[figure not shown]
SAP Version	Approval Date	Change	Rationale
0.1		Not applicable.	First draft
0.2		Response to the sponsor's comment on Draft version 0.1	Second draft
0.3		Response to sponsor's comments on Draft Version 0.2.	Third draft
1.0	22-Feb-2025	Finalized draft.	Finalized version

[figure not shown]

# **List of Abbreviations**

Abbreviation	Definition		
AE	adverse event		
ASA	American Statistical Association		
BID	twice daily		
BMI	body mass index		
CDISC	Clinical Data Interchange Standards Consortium		
CRF	case report form		
CSR	clinical study report		
DSMB	data safety monitoring board		
ED	early discontinuation		
EMA	European Medicines Agency		
ET	early termination		
FDA	Food and Drug Administration		
GCP	good clinical practice		
ICH	International Conference on Harmonization		
MedDRA	medical dictionary for regulatory activities		
PT	preferred term		
RSS	Royal Statistical Society		
SAE	serious adverse event		
SAF	safety analysis set		
SAP	statistical analysis plan		

Abbreviation	Definition	
SD	standard deviation	
SOC	system organ class	
TEAE	treatment-emergent adverse event	
TLF	table, listing and figure	

#### 1. Overview

This Statistical Analysis Plan (SAP) describes the planned analysis and reporting for Cassava Sciences, Inc. protocol number PTI-125-10 (An Open-Label, Long-Term Extension Study to Evaluate the Safety and Tolerability of Simufilam 100 mg Tablets in Participants with Mild to Moderate Alzheimer's Disease), dated 10-Nov-2023 and protocol version 3.0. Reference materials for this statistical plan include the protocol and the accompanying sample data collection documents. Operational aspects related to collection and timing of planned clinical assessments are not repeated in this SAP unless relevant to the planned analysis.

The structure and content of this SAP provides sufficient detail to meet the requirements identified by the Food and Drug Administration (FDA), European Medicines Agency (EMA), and International Conference on Harmonization (ICH) of Technical Requirements for Registration of Pharmaceuticals for Human Use: Guidance on Statistical Principles in Clinical Trials (ICH, 1998). All work planned and reported for this SAP will follow internationally accepted guidelines, published by the American Statistical Association (ASA, 2018) and the Royal Statistical Society (RSS, 2014), for statistical practice.

The planned analyses identified in this SAP may be included in clinical study reports (CSRs), regulatory submissions, or future manuscripts. Also, post-hoc exploratory analyses not necessarily identified in this SAP may be performed to further examine study data. Any post-hoc or unplanned, exploratory analysis performed will be clearly identified as such in the final CSR.

The statistical plan described hereafter is an *a priori* plan. The SAP will be finalized and approved prior to locking of the study database.

This document does not include the details of the planned analyses for the external Data Safety Monitoring Board (DSMB). The schedule of planned analyses is described in the DSMB charter and separate shells for tables, listings, and figures (TLF) are prepared for the DSMB meetings.

#### 2. Study Objectives and Endpoints

# 2.1. Study Objectives

# 2.1.1. Primary Objective

[figure not shown]
The primary objective of this study is to evaluate the long-term safety and tolerability of simufilam 100 mg tablets in subjects who have completed one of the two double-blind simufilam phase 3 studies.

# 2.2. Study Endpoints

#### 2.2.1. Safety Endpoints

The safety endpoints of this study include the following:

• Incidence of adverse events (AEs) including treatment-emergent, serious, related to study drug, and leading to withdrawal along with AEs by severity and relationship to study drug.

# 3. Overall Study Design and Plan

# 3.1. Overall Design

As background for the statistical methods presented below, this section provides an overview of the study design and plan of study execution. The protocol is the definitive reference for all matters discussed in what follows.

This is a multi-national, multi-center, fixed-dose, 52-week, open-label extension study to evaluate the long-term safety and tolerability of simufilam 100 mg tablets in subjects who have completed one of the two double blind simufilam phase 3 studies. Subjects from either of the two double-blind simufilam phase 3 studies (PTI-125-06 or PTI-125-07) rollover into this open-label extension study, provided that all inclusion and none of the exclusion criteria are met.

Once participants enrolled in the study, visits to the research clinic will occur at Weeks 4, 16, 28, 40 and 52.

Safety will be evaluated by adverse event monitoring at every visit.

An independent DSMB will meet periodically to review participant safety assessments and determine if dosing may continue. A charter was developed with specific guidance for the DSMB.

No interim analysis is planned for this study.

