A 26-week oral gavage carcinogenicity study of simufilam in CByB6F1-Tg (HRAS)2Jic mice is currently in the dosing phase, while a 104-week oral gavage carcinogenicity study of simufilam in rats started dosing in February 2022 and is currently in the reporting phase.

The drug substance impurity CML 1497 was qualified for safe clinical use in a 13-week repeat dose oral toxicity study in the rat and in *in vitro* genetic toxicity studies. A metabolite in safety testing (MIST) study evaluated the relative exposure of circulating human plasma metabolites to rat plasma metabolites based on peak area ratios. All six metabolites identified in human plasma were identified in the rat and adequate coverage based on peak area ratio ($AUC_{rat}/AUC_{human} \geq 0.5$) was demonstrated in the rat.

More information can be found in the Investigator's Brochure.

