4. SUMMARY OF STUDY DESIGN

This is a multi-national, multi-center, fixed-dose, open-label extension study that will continue through FDA approval of simufilam or program termination ([Appendix A](#)). After completing participation in either PTI-125-06 or PTI-125-07, subjects will have the option to participate in this study. After the subject provides consent and the Investigator confirms the subject satisfies both inclusion and exclusion (I/E) criteria, the study drug will be administered at the research site on Study Day 1 and subsequent visits will be scheduled.

Subjects who already completed participation through Week 52 in PTI-125-10 will have the option to return to the study and continue participation. After the subject provides consent, the Investigator will confirm that the subject continues to satisfy both the I/E

criteria. The study drug will be administered at the research site on Re-entry Day 1 and subsequent visits will be scheduled. The length of their participation gap will dictate which visits apply to them.

We anticipate up to 1,350 subjects may enroll in this study. Approximately 170 clinical sites in the USA, Canada, the Republic of Korea, and Australia will have the option to participate in this collaborative research effort.

For subjects electing to participate, the clinical and laboratory assessments from the Week 76 (PTI-125-06) or Week 52 (PTI-125-07) End-of-Treatment visit will serve as Baseline Visit assessments for the open-label study on Study Day 1. Additional blood samples will be taken on Study Day 1 to assess Hemoglobin A1c (HbA1c) and plasma biomarkers upon receipt of required supplies. All subjects will return in 4 weeks and then every 12 weeks thereafter for safety assessments.

For subjects re-entering the study, the length of their participation gap will determine their need for clinical and laboratory assessments. A blood sample will be taken to assess HbA1c and plasma biomarkers upon receipt of required supplies.

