12.5. CLINICAL DEMENTIA RATING

CDR sum of boxes and/or global score assessments measured repeatedly will be analyzed using a linear mixed model for repeated measurements. Two subject cohorts will be analyzed separately: those randomized to placebo in the PTI-125-06 or PTI-125-07 phase 3 studies, and those randomized to simufilam in those studies. Within-subject change from baseline may also be conducted. The analytical model and all other analyses will be fully described in the statistical analysis plan.

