# 10. Changes from Planned Analyses

Due to the early sponsor termination of PTI-125-10, the following analyses will no longer be tabulated/listed:

- Mean change in clinical laboratory values from baseline to Weeks 4, 28 and 52
- Mean change in vital signs (blood pressure [supine], temperature, pulse rate) from baseline to Weeks 4, 16, 28, 40, and 52
- Mean change in body weight from baseline to Weeks 4, 16, 28, 40, and 52

- Shifts in physical exam (PE) findings from baseline to Weeks 4, 16, 28, 40, and 52
- Shifts in neurological exam (NE) findings from baseline to Week 4, 16, 28, 40, and 52
- Mean change in ECG parameters from baseline to Weeks 4, 28, and 52
- Concomitant medications/treatments usage
- Shifts in the C-SSRS from baseline to Weeks 4, 16, 28, 40, and 52.
- Shifts in HbA1c values from baseline to Weeks 28 and Week 52. The analysis is done separately among subjects who were previously on placebo and simufilam in PTI-125-06 and PTI-125-07 phase 3 studies.

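### The SAP is written to a superseded 52-week protocol, leaves adverse event follow-up and exposure undefined, and does not declare the CDR and plasma biomarker models as dropped

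*SAP*

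**What the plan says.** **Design in the SAP.** Section 1 ties the plan to a protocol "dated 10-Nov-2023 and protocol version 3.0". Section 3.1 gives the length as "This is a multi-national, multi-center, fixed-dose, 52-week, open-label extension study" and says that "visits to the research clinic will occur at Weeks 4, 16, 28, 40 and 52". Table 1 in Section 3.7 stops at Week 52 and the Week 53 to 54 phone call.

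**Design in the current protocol.** Section 4 describes an "open-label extension study that will continue through FDA approval of simufilam or program termination". It also states: "Subjects who already completed participation through Week 52 in PTI-125-10 will have the option to return to the study and continue participation". Appendices B and C add Repeat Visits A and B, CDR and plasma biomarkers.

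**Endpoint.** SAP 2.2.1 has one endpoint, the incidence of adverse events. Under SAP 9.1 an event is treatment-emergent if it starts, or worsens, on or after the date of first dose; no closing date is given. SAP 4.1 sets the general denominator as the number of subjects. SAP 7.3, on exposure and compliance, is a heading with no text, and SAP Section 12 lists no exposure table or listing.

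**Analyses promised and dropped.** Protocol 12.3, 12.4 and 12.5 specify linear mixed models for HbA1c, plasma biomarkers and CDR. For CDR the protocol adds: "The analytical model and all other analyses will be fully described in the statistical analysis plan". SAP Section 10 opens with "Due to the early sponsor termination of PTI-125-10, the following analyses will no longer be tabulated/listed" and lists nine items. CDR and plasma biomarkers are not among them, and HbA1c is listed as shifts to Weeks 28 and 52.

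**The concern.** A SAP finalised in February 2025 should describe the study as it was by then conducted. If it describes an older 52-week version, two things follow.

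First, the one remaining endpoint has no defined follow-up. Subjects stopped early by the sponsor's termination, subjects who finished at Week 52, subjects who continued past it and subjects who left and returned would share one numerator and one denominator. Without exposure data, a reader could not tell what length of treatment a percentage refers to.

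Second, Section 10 reads as the full list of planned analyses that were not done. If it was built from version 3.0, analyses added by a later amendment drop out without being declared, and the study report would inherit that gap.

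**Working it through.** **1. Is the SAP's protocol the older one?** The version number of the current protocol is not in the text available, so this rests on content.
- Protocol 2.2 says of a 104-week rat study that it "started dosing in February 2022 and is currently in the reporting phase". February 2022 plus 104 weeks is about February 2024, which is after 10-Nov-2023.
- SAP Table 1 has a combined Week 52 and early-termination column, a Week 53 to 54 column, height at Study Day 1 only, and a footnote on HbA1c supplies. The protocol's summary of changes records each of these as replaced, extended or removed.
- SAP 9.1.2 merges two sets of causality categories across protocol amendments, so its authors expected data from more than one version.

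**2. Does the current schedule go past Week 52?** From Appendix B, for new and active participants:
- Repeat Visit A: 52 + 12 = Week 64, then every 24 weeks (88, 112, ...).
- Repeat Visit B: 64 + 12 = Week 76, then every 24 weeks (100, 124, ...).

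Re-entry subjects have Repeat Visit A at 12 weeks and Repeat Visit B at 24 weeks after Re-entry Day 1. None of these visits is in the SAP.

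**3. What does the event rule do with a re-entry subject?** The first dose is the one on Study Day 1. An event starting in the gap falls after that date, so it meets SAP 9.1. Protocol 7.1.2 collects adverse events and new medical conditions from the gap on Re-entry Day 1, so such events can reach the database. The SAP has no rule to set them apart.

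**4. How far can a per-subject percentage move?** The plan gives no sample size calculation, event rate or follow-up distribution, so there is no figure of its own to reproduce. The following is an illustration. Assume a constant hazard and a 52-week risk r = 10%. The risk by week w is 1 − (1 − r)^(w/52).
- 26 weeks: 1 − 0.9^0.5 = 5.1%
- 52 weeks: 10.0%
- 100 weeks: 1 − 0.9^(100/52) = 18.3%
- 104 weeks: 1 − 0.9^2 = 19.0%

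Applied to the 1081 participants in SAP 3.3, with assumed follow-up mixes:

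| Follow-up mix | Crude percentage | Subjects |
|---|---|---|
| All to Week 52 | 10.0% | 108 |
| Half to Week 52, half to Week 100 | (10.0 + 18.3)/2 = 14.2% | 153 |
| Half to Week 26, half to Week 52 | (5.1 + 10.0)/2 = 7.6% | 82 |
| Quarter to Week 26, half to Week 52, quarter to Week 100 | 10.9% | 117 |

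The underlying rate is the same in every row: −ln(0.9) = 0.105 per 52 weeks, or 10.5 per 100 person-years.

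**5. Would a 52-week onset cut be enough?** No. It brings the second row back to 10.0%, but the third row stays at 7.6%, because subjects stopped at Week 26 remain in the denominator. Person-time or interval-specific risk sets are needed as well.

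**6. Section 10 against the current protocol.**

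| Protocol analysis | In SAP Section 10? |
|---|---|
| Laboratory tests, vital signs (12.2) | Yes, with reason |
| HbA1c mixed model, including re-entry subjects (12.3) | Only as shifts to Weeks 28 and 52, split by prior placebo or simufilam |
| Plasma biomarker mixed models (12.4) | No |
| CDR mixed model (12.5) | No |

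Section 10 also records weight, physical and neurological examinations, ECG, concomitant medications and C-SSRS.

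**The case against.** The strongest reply is that the SAP is descriptive, calls its design section background, and makes the protocol the definitive reference. That softens the design mismatch. It does not supply the missing rules on exposure and the gap, and the protocol it names is version 3.0.

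Several stronger readings are tempting and are not supported.
- A reader might infer that adverse events will be presented as 52-week results. No endpoint, summary or table title states such a window. The defect is that the window is undefined, not that it is mislabelled.
- A reader might infer that protocol analyses vanish wholesale without record. Section 10 names nine, with early termination as the reason, and HbA1c is among them with the same two cohorts as the protocol. SAP 8.1 and 8.2 also say that no efficacy analysis is planned. What is missing is a line each for CDR and plasma biomarkers, and the HbA1c model.
- A reader might infer that biomarkers were measured and then left unanalysed. Collection was to start only once supplies arrived, and the protocol says which assays may be included. The documents show that sampling was scheduled, not that assays were done.
- A reader might infer a failed comparison with the parent studies. The SAP plans none, and a 52-week cut would not match the 76-week parent study in any case.

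It is also fair to say that the illustration rests on assumed risks and a constant hazard. With early termination, even the direction of any distortion is open. That stands, and it is a reason to report follow-up.

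**Conclusion.** The point holds in this form. The SAP rests on a superseded 52-week protocol. Its sole endpoint is a per-subject percentage with no end to the counting period, no rule for the re-entry gap and no exposure summary, so it pools unequal follow-up and, taken literally, admits gap events as treatment-emergent. The CDR and plasma biomarker mixed models are neither planned nor declared as dropped, and the HbA1c entry does not match the protocol's method.

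The size is unknown. The documents do not say how many subjects passed Week 52, re-entered or were cut short. The 5% to 19% range around an assumed 10% risk shows only that follow-up length matters. This should be corrected, but it does not show that any reported result is wrong.

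**What to change.** - Re-base SAP 1, 3.1, 3.7 and 10 on the current protocol, with its version and date.
- Fill SAP 7.3 with an exposure table: duration, person-years, number followed past Week 52 and number re-entered.
- Present treatment-emergent events as exposure-adjusted rates or by time interval, including onset within 52 weeks of first dose, and also over all on-drug follow-up.
- State a rule that separates events arising in the off-drug re-entry gap, and say how long after the last dose events are counted.
- List the CDR, plasma biomarker and HbA1c mixed models in Section 10 as protocol analyses not performed, with the reason.

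The documents do not give a lock date. If the database is already locked, declare these as changes in the clinical study report. The cost is a text revision, some extra programming and a few more tables. No new data are needed.
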